7.4. STATISTICAL TESTS

The default significant level will be (5%); confidence intervals (CIs) will be 95% and all tests will be two-sided, unless otherwise specified in the description of the analyses.

7.5. COMMON CALCULATIONS

For quantitative measurements, change from baseline will be calculated as:

- Test Value at Visit X – Baseline Value

7.6. SOFTWARE VERSION

All analyses will be conducted using SAS version 9.2 or higher.

8. STATISTICAL CONSIDERATIONS

8.1. MULTICENTER STUDIES

This study will be conducted at multiple hospital sites. Allocation to treatment arms is stratified by centre.

Centre pooling will be carried out across all centres for use in statistical summaries for this study. Centre will be

Document:	Reckitt Benckiser GA1210 Statistical Analysis Plan		
Author:	[REDACTED]	Version Number:	2.0

Version Date: 29Jul2014

Template No: CS_TP_BS016 – Revision 3

Reference: CS_WI_BS005

Effective Date: 01May2012

Page 11 of 23

included in the statistical models to adjust for centre effect. Treatment by centre interaction may also be explored using additional analyses. Refer to Section 15 for more details.

8.2. MISSING DATA

Patients who withdraw from the study will not be replaced.

Unless otherwise specified, all analysis will be based on the number of non-missing observations. If relevant for categorical tabulations, missing values will be treated as another category, so that all tabulations involving this variable will also include a row or column as appropriate to indicate the number of patients for whom the variable was recorded as a missing value.

For AEs, partial or missing dates and times will not be imputed, and this will be listed as originally reported in the Case Report Form (CRF).

8.3. EXAMINATION OF SUBGROUPS

No subgroup analyses will be performed for this study.

8.4. MULTIPLE COMPARISONS/ MULTIPLICITY

To preserve the type 1 error rate of 5% for the key secondary endpoint (change from baseline in RDQ scores for dyspepsia dimension), a closed testing procedure will be applied. A significant comparison at the 5% level ($p<0.05$) for this key secondary endpoint will only be deemed as confirmatory evidence if the primary endpoint is also significant at the 5% significance level ($p<0.05$). All other secondary endpoints and/or any further sensitivity or exploratory analyses for the primary and key secondary endpoint will serve as supportive evidence only and therefore no further adjustment for multiple comparisons will be made.

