7 STUDY RATIONALE

This study is being conducted to provide evidence for inclusion in applications to regulatory authorities that the Compound Sodium Alginate Double Action Chewable Tablets are effective in managing the symptoms of heartburn, acid regurgitation and dyspepsia in patients with GERD.

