8.2 Secondary Objective(s)

The secondary objectives of this study are to assess the efficacy of Compound Sodium Alginate Double Action Chewable Tablets compared with matching placebo in reduction of the symptoms of heartburn, acid regurgitation and dyspepsia in patients with GERD. Other secondary objectives include the efficacy of Compound Sodium Alginate Double Action Chewable Tablets compared with placebo in patient responsiveness / satisfaction and comparison of safety in terms of adverse events.

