14 STATISTICAL CONSIDERATIONS

The statistical analysis will be undertaken in collaboration with Quintiles.

A detailed Statistical Analysis Plan will be finalised before the code for all patients is broken and prior to analysis of the study being carried out.

Any deviations from the analyses described below will be included in the Statistical Analysis Plan, which will form Appendix 16.1.9 of the clinical study report.

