14.1 Sample Size Justification

In a previous pilot study conducted in the UK (GA1203), a least square mean difference (Gaviscon – Placebo) of -0.61 was obtained from the ANCOVA model comparing the change in the GERD dimension score from the RDQ after 1 week. The root mean squared error (RMSE) from the ANCOVA model, which included treatment as a fixed effect and the day 0 RDQ GERD dimension score as a covariate, was 0.9735.

In the same study, a least square mean difference (Gaviscon – Placebo) of -0.43 was obtained from the ANCOVA model comparing the change in the Dyspepsia dimension score from the RDQ after 1 week. The root mean squared error (RMSE) from the ANCOVA model, which included treatment as a fixed effect and the day 0 RDQ Dyspepsia dimension score as a covariate, was 1.121.

For the purposes of sample size estimation using the module for a two-group t-test between equal means in NQuery Advisor 7.0, the least square means difference and RMSE from GA1203 will be used to estimate the effect sizes. The effect sizes using these results would be estimated as 0.627 for the GERD dimension and 0.384 for the Dyspepsia dimension.

In other previous studies, different endpoints to the RDQ were used to demonstrate the efficacy of Gaviscon Original Liquid compared to Placebo Liquid. The percentage of patients that rated a positive improvement in symptoms were reported. In a study conducted in the UK (0900901), 74% of Gaviscon Original patients had a positive improvement of symptoms compared to only 44% of Placebo patients. When a similar study was conducted in China (GA0917), the corresponding results were 77% for Gaviscon Original and 67% for Placebo, thus suggesting an increased Placebo effect in the Chinese population compared to the UK population.

Assuming a reduced effect size of 0.2 for the Dyspepsia dimension, this would require a total of 1054 patients with evaluable dyspepsia data from the RDQ to have 90% power to show a statistical significant difference at the 5% level using a two-group t-test. The actual analysis method to be used would be an ANCOVA model with treatment as a fixed effect, centre as a random effect and the day 0 RDQ Dyspepsia dimension score as a covariate.

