If an effect size of 0.4 is assumed for the GERD dimension, a sample size of 1054 patients would give more than 99% power to show a statistical significant difference at the 5% level using a two-group t-test. The actual analysis method to be used would be an ANCOVA model with treatment as a fixed effect, centre as a random effect and the day 0 RDQ GERD dimension score as a covariate.

To allow for 5% drop outs, 1100 patients will be randomised to ensure that 1054 patients have evaluable data for the Dyspepsia dimension score.

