14.4.3 Statistical Methods for Efficacy Analyses

All statistical tests performed will be 2-tailed with significance assessed at the 5% significance level. The null hypothesis at all times will be the equality of the treatments being compared.

Normality assumptions will be evaluated by an examination of the residual plots. Depending on the degree of departure from these assumptions, an alternate nonparametric approach may be used for supportive purposes.

The primary endpoint (change in RDQ GERD dimension score) will be analysed using an analysis of covariance (ANCOVA) model with a fixed effect term for treatment, centre as a random effect and the day 0 RDQ GERD dimension score as a covariate. Treatment group differences will be estimated using the least square means and presented with 95% confidence intervals and p-values to make inferences.

The change in symptom score for each dimension separately will be analysed identically to the primary endpoint although the included covariate will be the relevant dimension day 0 score rather than the GERD dimension score.

To preserve the type 1 error rate of 5% for the key secondary endpoint (change from day 0 in RDQ scores for dyspepsia dimension), a closed testing procedure will be applied. A significant comparison at the 5% level ($p<0.05$) for this key secondary endpoint will only be deemed as confirmatory evidence if the primary endpoint is also significant at the 5% significance level ($p<0.05$). All other secondary endpoints and/or any further sensitivity or alternate analyses for the primary and key secondary endpoint will serve as supportive evidence only and therefore no further adjustment for multiple comparisons will be made.

For the primary and key secondary endpoint, two additional separate exploratory ANOVA models will be conducted identical to those stated above but with one additional interaction term for the treatment by centre interaction (random effect) and treatment by baseline covariate interaction respectively.

The change scores in frequency and intensity for each dimension as well as the two OTE responses will be compared between treatments using a Wilcoxon Rank Sum Test stratified by centre.

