18.3 Protocol Amendments

The investigator must abide by the agreed protocol as approved by the IEC/IRB.

No change will be made to the agreed protocol without the prior written approval of the Investigator, the Clinical Project Manager, the R&D Manager Clinical (Healthcare) and the Global Medical Director, except in circumstances where the immediate safety of the patient is at risk. Written approval will also be obtained from other functions if appropriate, for example the Statistician if the amendment relates to a change in endpoints.

All substantial protocol amendments require IEC/IRB and regulatory approval. Protocol amendments will be submitted to the same IEC/IRB and regulatory authority as the study protocol.

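### Before unblinding, heartburn and regurgitation could each have been added to the error-controlled sequence after dyspepsia, at no cost to the first two tests (optional improvement, lowest severity)

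*SAP*

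**What the plan says.** Protocol 14.4.3 and SAP 8.4 set out the same two-step procedure: the GERD dimension at the 5% level, then dyspepsia, which counts as confirmatory only if the GERD dimension is also significant. All remaining secondary endpoints fall outside it. The SAP states: "All other secondary endpoints and/or any further sensitivity or exploratory analyses for the primary and key secondary endpoint will serve as supportive evidence only". The protocol has near-identical wording: "any further sensitivity or alternate analyses for the primary and key secondary endpoint will serve as supportive evidence only".

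SAP Appendix 2 defines the GERD dimension as the mean of eight items, four on heartburn and four on regurgitation. SAP 15.2.1 lists the separate heartburn and regurgitation dimensions as other secondary endpoints. SAP 15.2.3 analyses both with the primary mixed model and their own baseline covariate, and the code in SAP 15.1.3 produces treatment differences with confidence limits.

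Protocol section 7 says the trial is to support applications that the tablets "are effective in managing the symptoms of heartburn, acid regurgitation and dyspepsia in patients with GERD". The secondary objective in protocol 8.2 is efficacy "in reduction of the symptoms of heartburn, acid regurgitation and dyspepsia in patients with GERD".

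**The concern.** Of the three symptoms named in the rationale, only dyspepsia has its own error-controlled test. A significant GERD dimension supports a conclusion on heartburn and regurgitation combined. It does not say which of the two responded, or whether both did. The trial can therefore win both confirmatory tests and still hold only supportive evidence on heartburn alone and on regurgitation alone.

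The analyses needed for the two separate conclusions are already fully specified. Only a testing rule is missing. What is at stake is a possible extra conclusion; the two existing ones are not in doubt.

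**Working it through.** **Inputs from the documents.** 527 patients per arm (protocol 9.4). Two-sided 5% (protocol 14.4.3). "Assuming a reduced effect size of 0.2 for the Dyspepsia dimension", with 90% power; "If an effect size of 0.4 is assumed for the GERD dimension", with power above 99% (both protocol 14.1). The pilot estimate for dyspepsia was 0.384 (protocol 14.1).

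**Assumptions.** The documents give no effect size for heartburn or regurgitation alone and no correlations. I took equal SDs, a heartburn-regurgitation correlation ρ of 0.3 to 0.7, and a correlation of dyspepsia with each component of 0 to 0.5.

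**1. The plan's own figures.** The noncentrality is d × √(527/2) = 16.233d, and the critical t on 1052 df is 1.962.

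| Test | d | Noncentrality | Power |
|---|---|---|---|
| Dyspepsia, planned | 0.20 | 3.247 | 90.0% |
| Dyspepsia, lower | 0.15 | 2.435 | 68.2% |
| Dyspepsia, lower | 0.10 | 1.623 | 36.8% |
| Dyspepsia, pilot | 0.384 | 6.233 | >99.9% |
| GERD dimension, planned | 0.40 | 6.493 | >99.9% |

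527 per arm is the smallest size that reaches 90% at 0.2 (526 gives 89.98%), so 1054 is reproduced exactly.

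**2. Error control of the extended sequence.** The proposed order is GERD dimension, then dyspepsia, then Holm on heartburn and regurgitation.
- If the GERD null is true, any later error requires a false rejection at step 1: at most 5%.
- If the GERD null is false and the dyspepsia null is true, any error requires a false rejection at step 2: at most 5%.
- If both are false, errors can arise only inside Holm: at most 5%.

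Simulation over null and partial-null configurations gave a maximum of 5% within simulation error. Steps 1 and 2 come first and keep their full 5%, so their power and the sample size are unchanged. By comparison, if the two symptoms were each read at 5% with no gate, the chance of at least one false positive when both are null and independent is 1 − 0.95² = 9.75%.

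**3. Gain under the planning assumptions.** The mean of two unit-SD scores has SD √((2+2ρ)/4), which is 0.806, 0.866 or 0.922 for ρ = 0.3, 0.5 or 0.7. If a composite effect of 0.4 is shared equally, each component effect is 0.4 times that SD: 0.322, 0.346 or 0.369. Each component then has power above 99.9%, so dyspepsia is the limiting step. With 1,000,000 simulated sets of test statistics per setting, all four tests succeed in about 90%, 68% or 37% of trials for a dyspepsia effect of 0.20, 0.15 or 0.10. Holm and a fixed order give the same result.

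**4. Two illustrative cases, both below the planned GERD effect.** Component effects of 0.2 and 0.2, or of 0 and 0.4, both average 0.2. The composite effect is 0.2/0.806 = 0.248 down to 0.2/0.922 = 0.217. GERD power is then 94-98%, and both gates together are passed in 85-89% of trials at dyspepsia 0.2.

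| Case (dyspepsia 0.2) | Outcome | Holm | Fixed order, heartburn first |
|---|---|---|---|
| 0.2 / 0.2 | heartburn confirmed | 79-82% | 80-83% |
| 0.2 / 0.2 | both confirmed | 74-79% | 74-79% |
| heartburn 0, regurgitation 0.4 | regurgitation confirmed | 85-89% | 2.5-3.6% |

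In the 0.2/0.2 case Holm costs heartburn at most about 1.5 points. In the 0/0.4 case a badly chosen order loses almost everything.

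**The case against.** The strongest reply is that there is no defect. The sponsor chose openly, and consistently in both documents, to stop at two confirmatory tests. All three symptoms already lie inside the controlled family, two through the GERD dimension and one through dyspepsia. The separate confidence intervals will show any divergence. All of that stands, and it is why this is an optional improvement.

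A reader might infer that type I error is not controlled, or that the protocol promised a confirmatory claim for each symptom and fails to deliver it. The documents support neither. The sequence is valid, and protocol 7 and 8.2 name the symptoms without promising separate error-controlled claims.

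A second reply is that the numbers favouring Holm come from invented cases. That is also fair. The 0.2/0.2 and 0/0.4 cases sit below the planned GERD effect, and nothing in the documents suggests that either symptom will fail to respond. In the planning case Holm and a fixed order are equivalent. The remaining argument for Holm is that the documents do not rank the two symptoms: the list in SAP 15.2.1 begins with OTE and is not a testing order.

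A third reply is that it is too late. For this trial, that is correct.

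**Conclusion.** The point holds at the lowest severity. The existing procedure is sound. It leaves heartburn and regurgitation confirmable only jointly, and both could have been added after dyspepsia without touching the alpha, sample size or power of the first two tests.

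The error-control result needs no assumption about effects or correlations. The size of the gain does: about 90% for both symptoms if the GERD effect is 0.4 shared equally and dyspepsia is 0.2, falling to about 68% or 37% if dyspepsia is 0.15 or 0.10. Under the current plan the chance of a confirmatory result on either symptom alone is zero by design.

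A reader might take the gain as assured whenever the two symptoms respond. It is not: if dyspepsia fails, nothing is added however strong they are. Nor may the sequence be extended now. The change form dated 01/SEP/2014 that follows the SAP refers to review of unblinded output.

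**What to change.** **Before unblinding only.** In SAP 8.4, add that once the GERD dimension and dyspepsia are both significant at two-sided 5%, the heartburn and regurgitation dimensions are tested with Holm: the smaller p-value against 0.025 and, if that succeeds, the other against 0.05. A prespecified fixed order at 5% each is equally valid if the sponsor can justify one. State that the added tests can be confirmatory only if dyspepsia succeeds. Leave OTE and the item-level analyses supportive.

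**Cost.** No extra patients, data or alpha. Protocol section 14 offers a route through the SAP: "Any deviations from the analyses described below will be included in the Statistical Analysis Plan". Whether that covers moving endpoints from supportive to confirmatory is a matter of reading, so the sponsor should confirm it. If protocol 14.4.3 is edited instead, the written approvals in protocol 18.3 apply, and "All substantial protocol amendments require IEC/IRB and regulatory approval".

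**After unblinding.** Make no change. SAP 8.4 stands as written, and heartburn and regurgitation are reported separately as supportive evidence.

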9. OUTPUT PRESENTATIONS

The templates provided with this SAP describe the presentations for this study and therefore the format and content of the summary tables, figures and listings to be provided by Quintiles Biostatistics.

Continuous variables will be summarized using descriptive statistics, i.e., number of subjects (n), mean, median, standard deviation, minimum and maximum.

Qualitative variables will be summarized by counts and percentages. Unless otherwise stated, the calculation of proportions will be based on the sample size of the population of interest.

Document: Reckitt Benckiser GA1210 Statistical Analysis Plan

Author: [REDACTED]

Version Number:

2.0

Version Date:

29Jul2014

Template No: CS_TP_BS016 – Revision 3

Reference: CS_WI_BS005

Effective Date: 01May2012

Page 12 of 23

10. DISPOSITION AND WITHDRAWALS

All subjects who provide informed consent will be accounted for in this study. The number of patients who provided informed consent, as well as those who were eligible will be summarized overall.

The number of patients who completed the study, the number of patients who withdrew prematurely from the study, the reasons for withdrawals and the number of patients in the AP, Safety, ITT and PP population will be summarized for each treatment group and overall.

Listings on patient completion/withdrawal information, as well as eligibility details will be reported.

Major protocol deviation will be summarized by treatment group and overall. Furthermore the number of patients to be excluded from each population together with reasons of exclusion will be summarized. Details on major protocol deviation as well as population classification information will be listed.

11. DEMOGRAPHIC AND OTHER BASELINE CHARACTERISTICS

Demographic data and other baseline characteristics will be summarized by treatment group and overall for all patients in AP. If there is a discrepancy in patient numbers between the AP and any other population, then baseline data will be summarised additionally for that population.

The following demographic and other baseline characteristics will be reported for this study:

- Age (years) –relative to date of consent
- Race
- Sex
- Height (cm)
- Weight (kg)
- Body mass index (BMI) (kg/m²)
- Smoking status – Yes, No, Former smoker
- Smoking years and amount (cigarettes per day)
- Alcohol use – Yes, No
- Drinking years and amount (gram per day)
- Drug of abuse history – Yes, No

Summary statistics will be presented for Investigator's assessment of patients' baseline GERD-related symptoms, including the severity of heartburn, regurgitation and dyspepsia.

In addition, interpretation of the 12-lead ECG results and abnormalities present in a standard hospital endoscopy examination will be reported at baseline as part of the screening procedures.

12. MEDICAL HISTORY AND CONCOMITANT ILLNESS

Medical History conditions are defined as those conditions which stopped prior to or at screening visit. Medical history information will be coded using version 17.0 of Medical Dictionary for Regulatory Activities (MedDRA) and presented for all patients in safety population by system organ class (SOC) and preferred term (PT), by treatment group and overall.

Concomitant illnesses are conditions other than GERD which are ongoing before or on the day of last dose of study drug, or stopped after screening visit but before or on the day of last dose of study drug. Concomitant illnesses will be captured from "Medical History and Current Status (excluding GERD)" form in eCRF, and will be coded using MedDRA version 17.0 and presented for all patients in safety population by SOC and PT, by treatment group and overall.

13. PRIOR AND CONCOMITANT MEDICATION AND THERAPIES

Medications will be coded using World Health Organization (WHO) Drug Dictionary Enhanced version dated 01Mar2013 and tabulated by indication collected on the eCRF(AE, Medical History, GERD, Endoscopy Related, Other), Anatomical Therapeutic Chemical (ATC) class and Standardized Medication Name for the safety population (for prior and concomitant medications separately)

- 'Prior' medications are medications which started and stopped prior to first dose of study medication.
- 'Concomitant' medications are medications which:
 - started prior to, on or after first dose of study medication
 - AND ended on or after first dose of study medication or were ongoing at the end of the study.

14. STUDY MEDICATION EXPOSURE & COMPLIANCE

The extent of exposure and compliance with study treatment will be presented for the safety population. Patients will receive Compound Sodium Alginate Double Action Chewable Tablets (two tablets four times daily) or matching placebo tablets for a period of 7 days.

14.1. DERIVATIONS

The date of first treatment administration will be the day after "date of dispense" on the eCRF "Drug Dispense" at Visit 2. The date of last treatment administration will be the day before the date of Visit 3 or Early Termination; for patients who do not have a Visit 3 or Early Termination date, the drug return date on the eCRF "Drug Return" will be used. Time on treatment in days will be derived from the following formula:

Document:	Reckitt Benckiser GA1210 Statistical Analysis Plan	Version Number:	2.0
Author:	[REDACTED]	Version Date:	29Jul2014

Template No: CS_TP_BS016 – Revision 3

Reference: CS_WI_BS005

Effective Date: 01May2012

Page 14 of 23

Time on treatment (days) = (date of Visit 3 or Early Termination or drug return date-1) – (date of dispense at Visit 2 +1) + 1

Compliance with study treatment is based on the drug accountability data recorded on the eCFR “Drug Dispense” and “Drug Return” forms and will be calculated as the number of tablets taken (total dispensed – total returned) divided by the prescribed number of tablets expressed as a percentage, see calculations below:

Θ = Prescribed number of tablets required to be taken per day, i.e., 8 tablets in this study.

$$\text{Compliance (\%)} = \frac{[\text{N of tablets dispensed at Visit2}]-[\text{N of tablets returned at Visit3 or Early Termination}]}{\text{Time treatment}(days)*\Theta} \times 100$$

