11.3.2.2 Clinical Assessments at Visit 3, End of Treatment

Visit 3 will take place preferably on the day following completion of 7-days of study treatment, ie, Day 8, or if necessary up to 1 day before and 2 days after that (Day 7 to Day 10). At this visit, the patient will complete the RDQ questionnaire and answer questions relating to overall satisfaction with the trial therapy (OTE) over the previous seven days. All unused and empty study medication containers will be returned for assessment of compliance with treatment. The following will be completed:

Vital Signs

- Blood pressure (after sitting for 5 minutes; mmHg).
- Heart rate (radial pulse counted for 30 seconds after resting for 5 minutes; beats/minute).

Concomitant Medication

- All concomitant medication usage including any OTC medications and traditional Chinese medicines will be recorded.

Adverse Events

- All adverse events will be recorded.

Physical examination

- A standard physical examination will be conducted.

Laboratory investigations

- Haematology
- Biochemistry

- Details are listed in section 13.4.

Pregnancy testing

- Women of child-bearing potential will undergo urine pregnancy testing.

11.3.2.3 Clinical Assessments at Early Termination (ET) Visit (only if required for patient early terminations)

The patient will be instructed to return to the investigator before the end of treatment if they require further treatment for their GERD symptoms or have unacceptable adverse events. Early termination applies to study Days 1 to 6. If the investigator withdraws the patient from the study for these or any other reasons the patient will complete the study at this early termination visit and the following will be completed.

The patient will complete the RDQ questionnaire and answer questions relating to overall satisfaction with the trial therapy (OTE) over the study treatment period. All unused and empty study medication containers will be returned for assessment of compliance with treatment. The following will be completed:

Vital Signs

- Blood pressure (after sitting for 5 minutes; mmHg).
- Heart rate (radial pulse counted for 30 seconds after resting for 5 minutes; beats/minute).

Concomitant Medication

- All concomitant medication usage including any OTC medications and traditional Chinese medicines will be recorded.

Adverse Events

- All adverse events will be recorded.

Physical examination

- A standard physical examination will be conducted.

Laboratory investigations

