11.9 Treatment Compliance

Treatment compliance will be assessed on the basis of tablet counts. Patients will be instructed to bring their unused IMP and any empty containers with them at each visit. For the time period between each visit, the number of unused tablets returned will be recorded. For the entire treatment period of the study, the proportion of tablets taken relative to the expected number of tablets that should have been taken will be calculated. A compliance to IMP intake of less than 75% will be considered a major protocol deviation. Patients with compliance of less than 75% will be excluded from the per protocol population.

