12.4 Dosage Instructions

Each patient will be instructed to thoroughly chew and swallow Compound Sodium Alginate Double Action Chewable Tablets or matching placebo tablets as a multiple dose regimen. Prior to dosing, all patients will be instructed by the Investigator on how they will take the

medication, ie, on each occasion take two tablets simultaneously, thoroughly chew and swallow both tablets. Patients will be instructed to start taking their medication the day after their randomisation visit for seven days (two tablets taken four times a day: 30 minutes after breakfast, 30 minutes after lunch, 30 minutes after dinner and immediately before lying down for bed).

Medication errors are reportable to RB irrespective of the presence of an associated AE/SAE, including:

- Medication errors involving subject exposure to a medicinal product
- Potential medication errors or uses outside of what is foreseen in the protocol that do or do not involve the participating subject.

Whether or not the medication error is accompanied by an AE/SAE, as determined by the investigator, the medication error and any associated AE/SAEs will be captured on an AE CRF page /SAE form (refer to Adverse Event Reporting section 13.1 for further details).

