12.5 Packaging

Sufficient IMP supplies will be packaged and labelled initially for 2000 patients (1000 patients per treatment group). This will allow for the initial allocation of 60 patients to each site. Each patient pack will contain 64 tablets (allowing 7 days study treatment and one days' overage).

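### The SAP 14.1 compliance denominator is not capped at the 56-tablet course, so a 75% score needs 48 tablets at a Day 9 visit and 54 at a Day 10 visit, not 42

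*SAP*

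**What the plan says.** Protocol 12.4 fixes the course: "Patients will be instructed to start taking their medication the day after their randomisation visit for seven days", two tablets four times a day. SAP 14 likewise describes active "or matching placebo tablets for a period of 7 days". Protocol 12.5 sets the supply: "Each patient pack will contain 64 tablets", which covers the seven days plus one spare day.

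Visit 3 is preferably on Day 8, "or if necessary up to 1 day before and 2 days after that (Day 7 to Day 10") under protocol 11.3.2.2. SAP 6.4 keeps the Day 7 to Day 10 window for the per-protocol (PP) population.

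Protocol 11.9 defines compliance over the whole treatment period: "the proportion of tablets taken relative to the expected number of tablets that should have been taken will be calculated". A result below 75% is a major deviation and excludes the patient from PP.

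SAP 14.1 describes the measure as tablets taken "divided by the prescribed number of tablets expressed as a percentage". The formula that follows uses eight tablets per day multiplied by time on treatment. It also states: "The date of last treatment administration will be the day before the date of Visit 3 or Early Termination". The duration is then "Time on treatment (days) = (date of Visit 3 or Early Termination or drug return date-1"), minus the day after dispensing, plus one. Neither document limits that duration to seven days.

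**The concern.** The text of SAP 14.1 and its formula agree only when Visit 3 falls on Day 8. After Day 8 the denominator keeps growing by eight tablets a day, although the patient was told to stop after seven days. For Day 9 and Day 10 visits the score therefore partly measures when the patient came back.

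The compliance summary for the safety population is affected directly. The effect on PP is an inference. SAP 14.1 holds the only compliance formula in the SAP, and protocol 11.9 ties the 75% rule to PP exclusion. If the formula set the flag, patients who took at least 75% of the course could have been recorded as major deviators and dropped from the PP sensitivity analyses in SAP 15.1.4 and 15.2.4.

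The derived last-dose date may also overstate time on treatment for Day 9 and Day 10 visits if patients stopped after Day 7 as instructed. Packs hold a spare day, so this is not certain.

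**Working it through.** **Inputs**
- Dispensing at Visit 2 = Day 0 (SAP 7.1; protocol 11.3.2.1)
- Eight tablets per day (SAP 14.1)
- Seven days of dosing (protocol 12.4)
- Permitted visit day V = 7 to 10 (protocol 11.3.2.2)
- PP cut-off 75% (protocol 11.9; SAP 6.4)

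**Stated figure reproduced.** Pack size = 8 × (7 + 1) = 64 tablets, as in protocol 12.5. The course without the spare day is 8 × 7 = 56, and 75% of it is 42 tablets.

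**SAP 14.1 as written**
- Time on treatment = (V − 1) − (0 + 1) + 1 = V − 1 days
- Denominator = 8(V − 1)
- Tablets needed for 75% = 0.75 × 8(V − 1) = 6(V − 1)

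| Visit day | Days counted | Denominator | Tablets for 75% | As % of 56 | Score for 42 tablets | Score for 56 tablets |
|---|---|---|---|---|---|---|
| 7 | 6 | 48 | 36 | 64.3% | 87.5% | 116.7% |
| 8 | 7 | 56 | 42 | 75.0% | 75.0% | 100.0% |
| 9 | 8 | 64 | 48 | 85.7% | 65.6% | 87.5% |
| 10 | 9 | 72 | 54 | 96.4% | 58.3% | 77.8% |

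On Day 10 a patient who emptied the pack would score 64/72 = 88.9%, so 100% cannot be reached.

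**With a cap**
- Denominator = 8 × min(7, V − 1) = 48, 56, 56, 56 for Days 7 to 10
- Cut-offs = 36, 42, 42, 42 tablets

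**Patients whose status differs** (at least 75% with the cap, below 75% as written)
- Days 7 and 8: none.
- Day 9: 42 to 47 tablets. In whole two-tablet doses, (56 − t)/2 gives 5 to 7 of 28 doses missed.
- Day 10: 42 to 53 tablets, or 2 to 7 of 28 doses missed.

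Visit-day and tablet-count distributions are not in the documents, so the number of such patients cannot be computed.

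**The case against.** The arithmetic is not in dispute; the case against is about consequence and remedy.

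- **PP link not shown.** SAP 6.4 and protocol 14.2 refer only to the returned tablet count and do not cite SAP 14.1. The denominator used at the blind review of 23 July 2014 is not recorded. This stands: the PP effect is conditional.
- **Small effect.** Anyone who took the full course passes on every permitted day, Day 8 is the preferred visit day, the formula is the same in both arms, and PP results are supportive only. This also stands and is why the point is minor.
- **The cap has its own assumption.** A patient who kept dosing until a Day 10 visit and took 42 tablets over nine days took 58.3% of the daily regimen, yet the cap gives 75.0%. Tablet counts cannot separate this patient from one who stopped on Day 7. The trade-off is real, but protocol 11.9 measures against what should have been taken, and no dosing instruction extends past seven days. The spare day does not explain a denominator of 72.
- **Day 7 is treated differently.** The cap leaves 48 tablets as the Day 7 denominator. That is defensible because the last day's doses may not yet be due at the visit, and it is not challenged here.
- **Two durations in one section.** Capping compliance but not exposure leaves an eight- or nine-day exposure beside a seven-day compliance base. A footnote discloses this without removing it.

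**Conclusion.** The point holds and is minor. As written, the formula departs from the SAP's own description of the denominator and from protocol 11.9 for every visit after Day 8. It raises the effective cut-off from 75.0% of the course to 85.7% on Day 9 and 96.4% on Day 10. These figures assume only dispensing on Day 0 and the instructed seven-day course.

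The error in the compliance table is certain for any Day 9 or Day 10 visit. Wrongful PP exclusion is possible only for partly compliant patients seen on those days, and only if SAP 14.1 set the flag. The ITT primary and key secondary analyses do not depend on it.

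**What to change.** 1. In SAP 14.1, for compliance only, set the denominator to 8 × min(7, Visit 3, early termination or drug return date − dispense date − 1). Report compliance as not calculable when the day count is 0 or less, as for an early termination visit on Day 1.
2. Show scores above 100% as they are (up to 64/56 = 114.3% from Day 8), as a sign that spare tablets were used.
3. Record which denominator was used at the blind review. State in SAP 6.4 that the 75% rule uses the capped formula, re-derive the flag mechanically for all patients and count those whose status changes.
4. If the data are already unblinded, as the change form dated 1 September 2014 at the end of the SAP indicates, keep the authorised PP set. If membership changes, report the corrected set as a labelled additional analysis with a documented change.
5. Leave the adverse-event window and the last-dose derivation alone. Add a footnote to the exposure table that time on treatment may be overstated for Day 9 and Day 10 visits.

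The cost is low: one denominator, one cross-reference, one footnote and a rerun of the compliance flag and table. It needs no new data and changes no ITT or adverse-event output. After unblinding it also needs a change form and, only if PP membership changes, one extra set of PP tables.
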